8.0 Dosage Modification Based on Adverse Events

Strictly follow the modifications in this table for the first **two** cycles, until individual treatment tolerance can be ascertained. Individual drugs can be dose reduced as per the table below depending on the adverse event attribution. Thereafter, these modifications should be regarded as guidelines to produce mild-to-moderate, but not debilitating, side effects. If multiple adverse events are seen, administer dose based on greatest reduction required for any single adverse event observed. Reductions apply to treatment given in the preceding cycle and are based on adverse events observed since the prior dose.

NOTE: If either of pomalidomide or ixazomib is discontinued, the patient can continue on the other drugs, unless specified otherwise in the dose modification tables. If both are discontinued, the patient will go to event monitoring (Section 18.0).

ALERT: ADR reporting may be required for some adverse events (See Section 10)

8.1 Dose Levels for each drug in the combination (Based on Adverse Events in Tables 8.2-4)

NOTE: One drug can be reduced each time based on the drug most likely related to the toxicity observed.

Ixazomib (Days 1, 8, 15)		Pomalidomide (Day 1-21)		Dexamethasone (Days 1, 8, 15, 22)	
Starting dose	4 mg	Starting dose	4 mg	Starting dose	40 mg
-1	3 mg	-1	3 mg	-1	20 mg
-2	2.3 mg	-2	2 mg	-2	12 mg
-3	2.3 mg days 1, 15	-3	1 mg	-3	4 mg
-4	Discontinue	-4	Discontinue	-4	Discontinue

If patients cannot tolerate dose level – 3 of ixazomib AND pomalidomide they will go to event monitoring per Section 18.0. If dexamethasone is discontinued, the patient may continue treatment.

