8.11 Instruction for initiation of a new cycle of therapy

A new cycle of treatment may begin on the scheduled Day 1 of a new cycle if:

- The ANC is $\geq 1000/\mu\text{L}$
- The platelet count is $\geq 50,000/\mu\text{L}$
- Any other non-hematologic treatment -related adverse event that may have occurred has resolved to \leq Grade 1 or baseline severity.

If these conditions are not met on Day 1 of a new cycle, the subject will be evaluated weekly and a new cycle of therapy will be held until the toxicity has resolved as described above.

If any drug dosing was halted during the previous cycle and was restarted with a one-level dose reduction without requiring an interruption for the remainder of the cycle, then that reduced dose level will be initiated on Day 1 of the new cycle.

If any drug dosing was omitted for the remainder of the previous cycle or if the new cycle is held due to known hematologic toxicity newly encountered on the scheduled Day 1, then the new cycle will be started with a one-level dose reduction. If a new cycle of therapy cannot be restarted within 4 weeks of the scheduled Day 1 due to non-resolution of drug related toxicities, the patient will be removed from protocol therapy and will go to event monitoring.

→ → Use the NCI Common Terminology Criteria for Adverse Events (CTCAE) version 4.0* unless otherwise specified ← ←

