8.2 Dose modifications for ixazomib based on adverse events during a cycle

CTCAE System/Organ/Class (SOC)	ADVERSE EVENT	AGENT[#]	ACTION**
Investigations	If platelet count $<30 \times 10^9/L$ or ANC $<1.0 \times 10^9/L$ or ANC $>1.0 \times 10^9/L$ (up to LLN) with fever (temperature $>38.5^\circ C$)	Ixazomib	Days 2-15: Ixazomib dose should be omitted. Complete blood count (CBC) with differential should be followed weekly. If ANC is $\geq 1.0 \times 10^9/L$ and/or platelet counts $\geq 30 \times 10^9/L$, ixazomib may be reinitiated with 1 dose level reduction (see Table 8.1). The subsequent cycle will use the reduced dose.
Skin and subcutaneous tissue disorders	Rash, maculopapular, \geq Grade 2	Ixazomib	Omit ixazomib till rash resolves to \leq Grade 1 (See Section 9.9a). Restart at same dose. If the rash recurs, reduce dose by one dose level.
	Any skin, Grade 4		Discontinue ixazomib
Nervous System Disorders	Newly developed Grade 1 peripheral neuropathy with pain, \geq Grade 2 peripheral neuropathy,	Ixazomib	Reduce dose of ixazomib to the next lower dose level
	Grade 2 neuropathy with pain or Grade 3 peripheral neuropathy	Ixazomib	Omit ixazomib until toxicity resolves or returns to baseline. When toxicity resolves, re-initiate ixazomib at the next lower dose level.

Table 8.2			
CTCAE System/Organ/Class (SOC)	ADVERSE EVENT	AGENT[#]	ACTION^{**}
	Grade 4 peripheral neuropathy	Ixazomib	Omit ixazomib. Peripheral neuropathy should be monitored until toxicity resolves or returns to baseline. Upon recovery, if the patient has received clinical benefit from therapy with ixazomib, the investigator may consider restarting ixazomib at the next lower dose level.
Other	Any other non-hematological Grade 3 attributable toxicity except: Grade 3 nausea and/or emesis in the absence of optimal anti-emetic prophylaxis Grade 3 diarrhea that occurs in the absence of optimal supportive therapy Grade 3 fatigue	Ixazomib Pomalidomide	Omit ixazomib or pomalidomide or both depending on the attribution to either or both drugs, until resolution to Grade ≤ 1 or baseline Restart at next lower dose - If a patient is already at the lowest drug level, go to event monitoring If the toxicity can be attributed to either of the drugs, pomalidomide should be discontinued at first instance followed by ixazomib for recurrence of the same toxicity necessitating dose modification

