9.8 Prohibited medications

Systemic treatment with any of the following metabolizing enzyme inducers should be avoided, unless there is no appropriate alternative medication for the patient's use. (Rationale: Unlike with inhibitors if there were to be a drug-drug interaction with an inducer, MLN2238 exposure would be less - so there is a reduced chance of an adverse event. However, there may be less chance for an antitumor effect, but that is not an absolute reason to be taken off ixazomib):

- Strong CYP3A inducers: rifampin, rifapentine, rifabutin, carbamazepine, phenytoin, and phenobarbital

Extra caution should be exercised when using these medications concomitantly and incidence of any side effects should be carefully monitored. Because these medications are constantly changing, please review any medications for their potential to induce CYP3A4. Potential resources may include the FDA and/or IUPUI websites, or your local institution's pharmacist.

Excluded foods and dietary supplements include St. John's wort and Ginkgo biloba.

9.9a Erythematous Rash with or without Pruritus:

As with bortezomib, rash with or without pruritus has been reported with ixazomib, primarily at the higher doses tested and when given with agents where rash is an overlapping toxicity. The rash may range from limited erythematous areas, macular and/or small papular bumps that may or may not be pruritic over a few areas of the body, to a more generalized eruption that is predominately on the trunk or extremities. Rash has been most commonly characterized as maculopapular or macular. To date, when it does occur, rash is most commonly reported within the first 3 cycles of therapy. The rash is often transient, self-limiting, and is typically Grade 1 to 2 in severity.

Symptomatic measures such as antihistamines or corticosteroids (oral or topical) have been successfully used to manage rash and have been used prophylactically in subsequent cycles. The use of a topical, IV, or oral steroid (e.g., prednisone ≤ 10 mg per day or equivalent) is permitted. Management of a Grade 3 rash may require intravenous antihistamines or corticosteroids. Administration of ixazomib (and/or other causative agent if given in combination) should be modified per protocol and re-initiated at a reduced level from where rash was noted (also, per protocol).

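### For a first Grade 2 or 3 maculopapular rash attributed to ixazomib, Table 8.2 restarts at the same dose, while Section 9.9a, and Section 8.11 in some cases, require a reduced dose

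*Combined protocol and SAP*

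**What the plan says.** Four places in the protocol bear on restarting ixazomib after a rash.

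- **Table 8.2, skin row.** For maculopapular rash of Grade 2 or higher, ixazomib is withheld until the rash is Grade 1 or lower. The row then points to the rash section and gives the restart rule: "Restart at same dose. If the rash recurs, reduce dose by one dose level". Grade 4 skin events have their own row, so this one operates at Grades 2 and 3.
- **Section 9.9a.** Ixazomib, or another causative agent in the combination, "should be modified per protocol and re-initiated at a reduced level from where rash was noted (also, per protocol"). First and recurrent rash are not distinguished.
- **Section 8.11.** "If any drug dosing was omitted for the remainder of the previous cycle", the next cycle starts one dose level lower. A first rash is not exempted.
- **Section 8.0.** "Strictly follow the modifications in this table for the first" two cycles; after that the modifications are guidelines.

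Table 7.1 gives ixazomib 4 mg on Days 1, 8 and 15, and Section 8.1 sets the first reduction at 3 mg.

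**The concern.** A site that sees a first Grade 2 or 3 maculopapular rash and attributes it to ixazomib finds two different restart doses, depending on whether it reads the dose-modification table or the rash section to which the table points. In some cases a third provision, on starting a new cycle, also departs from the table. Sites could treat the same event differently while each follows a written instruction.

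What is at stake is consistent dosing, and a clean reading of ixazomib exposure and tolerability. Toxicity of the combination is a secondary goal (Section 2.21), and Section 16.323 tabulates the maximum grade of each event per patient. A recurrence after restart would change that table only if its grade were higher than before. The timing makes the conflict practical: Section 9.9a says that "rash is most commonly reported within the first 3 cycles of therapy", whereas the tables bind strictly for two.

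**Working it through.** The plan states no figure on this point, so the check is to apply the three instructions to the same patient. Take someone on 4 mg with a first Grade 2 maculopapular rash attributed to ixazomib. Under the footnote to Table 8.2, an omitted dose is skipped and not made up.

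| Case | Table 8.2 | Section 9.9a | Section 8.11 |
|---|---|---|---|
| A. Onset Day 3, Day 8 dose omitted, Grade 1 by Day 15 | 4 mg on Day 15 | 3 mg on Day 15 | Not triggered |
| B. Onset Day 10, Day 15 dose omitted, Grade 1 before the next cycle | 4 mg at next Day 1 | 3 mg at next Day 1 | 3 mg at next Day 1 |
| C. Recurrence after restart at 4 mg | 3 mg | 3 mg | 3 mg if triggered |

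The 3 mg entries under Section 9.9a take its reduced level to mean one dose level, which the section does not itself state.

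In case A, Table 8.2 and Section 9.9a disagree. In case B, Section 8.11 also disagrees with Table 8.2: Day 15 is the last ixazomib dose of the cycle, so missing it means that the drug was omitted for the remainder. In case C there is no conflict. The problem is therefore confined to the first episode.

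**Does another provision settle it?** Section 8.0 gives the tables strict force in cycles 1 and 2, which favours Table 8.2 over Section 9.9a there but not from cycle 3 on. It does not settle Table 8.2 against Section 8.11, which sits in the same chapter and is written as mandatory.

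**Rash attributed to both drugs.** The note under Tables 8.2 and 8.3 has only one drug reduced per incidence, beginning with pomalidomide, and Table 8.3 restarts pomalidomide one level lower after Grade 2 or 3 rash. Reducing pomalidomide first and ixazomib on recurrence fits Table 8.2, and it fits the wording of Section 9.9a about another causative agent. The conflict is thus limited to rash attributed to ixazomib.

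**Dose difference.** (4 − 3) / 4 = 25% of each ixazomib dose from the starting level, or 3 × 4 = 12 mg versus 3 × 3 = 9 mg in a full cycle, until any later modification.

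**How many patients.** The documents give no rate for Grade 2 or higher maculopapular rash on this regimen. The possible proxies are all assumptions:

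- Table 1-3, oral combination studies, maculopapular rash of any grade: 29 / 173 = 16.8%; 0.168 × 27 = 4.5 patients.
- Section 15.17, ixazomib drug information, maculo-papular rash at 1% to under 10%: 0.01 × 27 = 0.3 to 0.10 × 27 = 2.7 patients.

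The Table 1-3 figure is the closest in event term and setting. It includes Grade 1, so the number meeting the Table 8.2 trigger would be lower if that rate applied.

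**The case against.** The best defence is that the text signals precedence. Section 9.9a belongs to the supportive-care chapter and defers to the protocol twice in one sentence, while Section 8.0 tells sites to follow the tables strictly. The pointer in Table 8.2 is attached to the instruction to withhold, not to the restart rule, so it may only send the reader to rash management. Much of this stands. A reader might infer that the references are circular and that nothing governs; the documents do not support that, at least for the first two cycles. But deferring to the protocol does not cancel the explicit words about a reduced level. Sections 9.9b and 9.9c use similar words, cite Table 8.2 by name, and agree with its haematologic row. Section 9.9a names no table and disagrees with its row.

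A second defence is that Section 9.9a concerns only severe rash, because the preceding sentence reads "Management of a Grade 3 rash may require intravenous antihistamines or corticosteroids". The dosing sentence carries no grade limit, and the Table 8.2 row includes Grade 3, so a conflict would remain at Grade 3 even on that reading.

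A third is that the matter is small. A reader might apply the statement in Section 1.3 that about 50% of patients have rash and infer 0.50 × 27 = 13.5 patients affected. That rate covers every type and grade of rash, comes from other ixazomib regimens, and cannot be applied to a row limited to maculopapular rash of Grade 2 or higher. A reader might also infer that rash is the overlapping toxicity expected most. Sections 15.17 and 15.27 list rash at 1% to under 10% for each drug and place several other shared toxicities in the very common group. These points reduce the size of the issue but do not remove the contradiction.

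**Conclusion.** The contradiction is real and narrow. For a first maculopapular rash of Grade 2 or 3 attributed to ixazomib, Table 8.2 and Section 9.9a give different restart doses. When ixazomib was omitted for the rest of the cycle, Section 8.11 also departs from Table 8.2. Recurrent rash is not affected, and rash attributed to both drugs can be handled consistently through the alternation note and Table 8.3.

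The difference is one dose level. It would be wrong to read it as a fixed 25% in every later dose: that figure holds from the 4 mg level only, and only until another change. The number of patients is uncertain: about 4 to 5 of 27 for rash of any grade if the Table 1-3 rate applied, and fewer at the triggering grade.

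This is a problem of consistent dosing and safety management. The response thresholds, sample size and error rates in Sections 16.21 to 16.24 do not depend on it.

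**What to change.** The sponsor should reconcile Table 8.2, Section 9.9a and Section 8.11 to one restart rule for a first rash attributed to ixazomib, and state which section governs if wording differs. The revised text should say whether first and recurrent rash are treated differently, whether the rule depends on grade, and how it applies when ixazomib was omitted for the rest of a cycle. Section 9.9a should cite the governing table by number, as Sections 9.9b and 9.9c do. No view is given here on which rule is right.

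The cost is a sentence or two in each place. Changing only Table 8.2 or only Section 9.9a may leave the disagreement with Section 8.11. If patients with such a rash have already been treated, the report should list the restart dose that each received. No design figure needs to be recalculated.

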8.3 Dose modifications for pomalidomide based on adverse events during a cycle

Table 8.3			
CTCAE System/Organ/Class (SOC)	ADVERSE EVENT	AGENT	ACTION**
Blood and lymphatic system disorders	Febrile neutropenia associated with fever ($\geq 38.5^{\circ}\text{C}$)	Pomalidomide	
 • Omit pomalidomide dose. • Follow CBC weekly. • If neutropenia has resolved to \leqGrade 2 prior to Day 21 and fever has resolved, restart pomalidomide at next lower dose level and continue the cycle through Day 21 • If febrile neutropenia is the only toxicity for which a dose reduction is required G-CSF may be used and the pomalidomide dose maintained
Investigations	Grade 3 neutrophil decreased and sustained for 7 days or Grade 4 neutropenia Platelet count decreased \geq Grade 3 (platelet count $< 50,000/\text{mm}^3$)	Pomalidomide	
 • Omit pomalidomide dose. • Follow CBC weekly. • Hold anticoagulation until platelets $\geq 50,000/\text{mm}^3$ • If platelet count resolves to \leqGrade 2 prior to Day 21, restart pomalidomide at next lower dose level and continue the cycle through Day 21 • If neutropenia has resolved to \leqGrade 2 prior to Day 21, restart pomalidomide at next lower dose level and continue the cycle through Day 21 • If neutropenia is the only toxicity for which a dose reduction is required G-CSF may be used and the pomalidomide dose maintained
Skin and subcutaneous tissue disorders	Rash maculopapular Grade 2 or 3	Pomalidomide	
 • Omit pomalidomide dose; follow weekly • If the toxicity resolves to \leqGrade 1 prior to Day 21, restart pomalidomide at next lower dose level and continue the cycle through Day 21
	Any rash Grade 4	Pomalidomide	
 • Discontinue pomalidomide and remove patient from all study treatment
Nervous system disorders	Peripheral sensory neuropathy Grade 3	Pomalidomide	
 • Omit pomalidomide dose and follow at least weekly • If the toxicity resolves to \leqGrade 1 prior to Day 21, restart pomalidomide at next lower dose level and continue the cycle through Day 21

Table 8.3			
CTCAE System/Organ/Class (SOC)	ADVERSE EVENT	AGENT	ACTION**
	Grade 4	Pomalidomide	
 Discontinue pomalidomide and remove patient from all study treatment

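### Table 8.2 gives two instructions for one neuropathy event, and Tables 8.2 and 8.3 disagree on Grade 4 sensory neuropathy attributed to both drugs

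*Combined protocol and SAP*

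**What the plan says.** Protocol Section 8.2, Table 8.2 (ixazomib), has three neuropathy rows.

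- Row 1 is triggered by "Newly developed Grade 1 peripheral neuropathy with pain" and, in the same cell, by any peripheral neuropathy of Grade 2 or higher. Action: "Reduce dose of ixazomib to the next lower dose level". No interruption is mentioned.
- Row 2 is triggered by "Grade 2 neuropathy with pain or Grade 3 peripheral neuropathy". Action: "Omit ixazomib until toxicity resolves or returns to baseline", then restart one level lower.
- Row 3 is Grade 4. Ixazomib is omitted and, after recovery and if the patient has benefited, "the investigator may consider restarting ixazomib at the next lower dose level".

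The table notes define an omitted dose as skipped and not made up. A further row of Table 8.2, for Grade 4 non-hematologic toxicity in general, names both drugs. It stops pomalidomide permanently and lets ixazomib continue if the investigator sees clinical benefit.

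Section 8.3, Table 8.3 (pomalidomide), deals with peripheral sensory neuropathy. Its Grade 4 action is "Discontinue pomalidomide and remove patient from all study treatment".

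On the force of the tables, Section 8.0 says "Strictly follow the modifications in this table for the first" two cycles; after that they are guidelines.

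**The concern.** A dose-modification table should send each event to one action. Here Grade 2 with pain and Grade 3 each meet two rows, and Grade 4 meets at least two. For Grade 4 sensory neuropathy in which both drugs are implicated, one table leaves a route back to ixazomib and the other ends all study treatment.

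The situation can arise. Exclusion 3.25 bars Grade 3 or higher neuropathy and painful Grade 2, so a patient may enter with painless Grade 2; if pain develops, that patient meets both rows. Neuropathy is listed as very common for both drugs (Sections 15.17 and 15.27), so joint attribution is realistic. More than one institution takes part (Sections 6.12 and 7.4), and discretion is not offered in Cycles 1 and 2. At stake are consistent patient management, ixazomib exposure and time on treatment.

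**Working it through.** No figure in the plan is in question, so the check is a mapping: each event is set against every row whose trigger it meets.

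| Event | Rows met | Ixazomib action |
|---|---|---|
| New Grade 1 with pain | Table 8.2 row 1 | Reduce |
| Grade 2 without pain | Row 1 | Reduce |
| Grade 2 with pain | Rows 1 and 2 | Reduce; or omit, then restart one level lower |
| Grade 3 | Rows 1 and 2 | Reduce; or omit, then restart one level lower |
| Grade 4, attributed to ixazomib | Row 1 (literally) and row 3; possibly the general Grade 4 row | Reduce; or omit with possible restart; or possibly continue if benefit |
| Grade 4 sensory, attributed to both drugs or not assignable | As above, plus Table 8.3 | As above, or removal from all study treatment |

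**Size of the Grade 2 with pain and Grade 3 conflict.** Both rows end one level lower. Ixazomib is given on Days 1, 8 and 15, so for an event after the Day 1 dose the within-cycle difference is at most 3 − 1 = 2 weekly doses. Section 8.11 then holds any new cycle until non-hematologic treatment-related events are at Grade 1 or less, or baseline. That narrows the difference between cycles. It may not close it, because row 2 waits for resolution or baseline, which could be read as stricter than Grade 1.

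**Search for a resolving rule.**

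1. Section 8.0 applies the greatest reduction when several adverse events occur. It does not address one event meeting two rows, and the reduction is the same in both rows.
2. Section 8.0 lets the other drugs continue after pomalidomide or ixazomib stops unless a table specifies otherwise. Table 8.3 does so, but nothing says whether it overrides Table 8.2 when both apply.
3. The note in Section 8.1 directs reduction to the drug most likely responsible. It does not help when neither can be singled out.
4. The note under Tables 8.2 and 8.3 on toxicity attributable to both drugs alternates dose reductions, starting with pomalidomide. It does not cover restart against removal.
5. Section 8.11 governs the start of a cycle, not the choice of row within one.

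None of these settles either conflict.

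**The case against.** The strongest answer has five parts.

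- **The specific row governs.** The rows rise in severity, and a clinician would naturally apply the narrower one. That is a sensible reading, but the protocol does not state it.
- **Attribution chooses the table.** This stands for single-drug events: if the event is attributed to ixazomib alone, Table 8.2 can govern by itself. A reader might infer that the tables clash for every Grade 4 neuropathy because both drugs list the toxicity. The documents do not support that. The clash is confined to sensory events attributed to both drugs or not assignable.
- **Table 8.2 is only permissive at Grade 4.** Removing the patient would breach neither table. True, but a site that used the permitted restart would breach Table 8.3, and the general Grade 4 row, which names both drugs, also contemplates continuing ixazomib.
- **Endpoints are little affected.** Section 16.323 records the maximum grade and Section 16.52 counts related Grade 4 or higher events. The dose action does not change a grade already recorded. This stands.
- **Few patients are involved.** This probably stands. Section 1.5 reports Grade 3 or 4 neuropathy in under 5% of 60 patients on pomalidomide and dexamethasone. If that carried over, it would be fewer than 0.05 × 27 = 1.35 of the 27 evaluable patients. That regimen had no ixazomib, and the figure omits painful Grade 2, so it is indicative only.

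A reader might also infer the same contradiction for Grade 4 skin events, since the Table 8.2 skin row names only ixazomib while Table 8.3 ends all treatment for Grade 4 rash. That is doubtful: if the general Grade 4 row applies alongside the skin row, pomalidomide stops too, and with both drugs stopped the patient goes to event monitoring.

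**Conclusion.** The point holds within limits. Inside Table 8.2, Grade 2 with pain and Grade 3 carry two instructions that reach the same dose level but differ on whether dosing is first interrupted. A reader might call these opposite managements; the shared end point does not support that. Grade 4 also falls literally in the reduce row. Across tables, jointly attributed or unassignable Grade 4 sensory neuropathy meets both a possible ixazomib restart and removal from all treatment, with no stated precedence.

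The number of affected patients cannot be derived. It is tempting to apply the 26% neuropathy rate (45 of 173) from the oral combination studies in Table 1-3, but that is an all-grade rate from combinations without pomalidomide. Affected events are likely few, and no effect on the primary decision rule is shown. The case rests on the contradiction, on its bearing on safety and exposure, and on the strict adherence required in Cycles 1 and 2.

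Two assumptions apply. The row 1 trigger is taken as complete, although its extracted text ends in a comma; any limiting words lost there would weaken the first part. The Table 8.3 Grade 4 entry is read as belonging to the sensory neuropathy heading directly above it.

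**What to change.** Reconcile Tables 8.2 and 8.3 by amendment.

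- Make the Table 8.2 neuropathy rows mutually exclusive by grade and pain status, so that each event has one action.
- State which table governs Grade 4 peripheral sensory neuropathy attributed to both drugs or not assignable to one, and whether the general Grade 4 non-hematologic row applies to neuropathy at all.
- For Grade 4 skin events, only clarify whether that general row applies alongside the skin row.

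Which action is right in each case is for the sponsor to decide. The cost is table wording in an amendment and notice to sites. Sample size, decision rules and analyses do not change.

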- 1.3 ***Ixazomib***: Ixazomib, which has been formulated for both intravenous (IV) and oral (PO) administration, is a small molecule proteasome inhibitor. It is the citrate ester of the biologically active boronic acid form, MLN2238, which is structurally similar to bortezomib. In water or aqueous systems, ixazomib rapidly hydrolyzes to MLN2238, therefore all doses and concentrations are expressed as MLN2238. Nonclinical studies were conducted with a solution of either MLN2238 or MLN2238 in equilibrium with ixazomib. Similar to bortezomib, MLN2238 potently, reversibly, and selectively inhibits the 20S proteasome. However in contrast to bortezomib, it has a shorter dissociation half-life ($t_{1/2}$) that may contribute to increased tissue distribution. Bortezomib has a slowly reversible dissociation rate from the red blood cell proteasome, while MLN2238 demonstrates a more rapidly reversible dissociation rate from the blood but sustained effects on bone marrow and tumor proteasomes suggesting better tissue distribution. The pharmacologic implications of this difference in binding kinetics and tissue distribution may in turn result in differences in safety and efficacy profiles in a broader range of tumors. In xenograft-bearing mice, the more rapid dissociation rate correlates with an increased ratio of tumor proteasome inhibition to blood proteasome inhibition, and ixazomib shows greater antitumor activity in several xenograft models, both solid tumor and bortezomib-resistant xenografts, than bortezomib.

Nonclinical Pharmacology: MLN2238 refers to the biologically active, boronic acid form of the drug substance, ixazomib. Ixazomib refers to the citrate ester of MLN2238. In water or aqueous systems, the equilibrium shifts from ixazomib to the biologically active boronic acid form MLN2238. All doses and concentrations are expressed as the boronic acid, MLN2238.

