	Grade 4 Nonhematologic Toxicities	Ixazomib Pomalidomide	Permanently discontinue pomalidomide. Consider permanently discontinuing ixazomib – Exception if the investigator determines the patient is obtaining a clinical benefit If both ixazomib and pomalidomide are discontinued, the patient will go to event monitoring

* Located [REDACTED]

** Use the following to describe actions in the Action column:

- Omit = The current dose(s) for the specified drug(s) during a cycle is skipped. The patient does not make up the omitted dose(s) at a later time
- Hold/Delay = The current dose(s) of all drugs during a cycle is delayed. The patient does make up the delayed dose(s) when the patient meets the protocol criteria to restart drugs.
- Discontinue = The specified drug(s) are totally stopped.

NOTE: For toxicities attributable to both ixazomib and pomalidomide, only one of the drugs should be reduced for each incidence of toxicity severe enough to necessitate dose reduction. The drug reduced should alternate starting with pomalidomide for the first dose reduction.

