15.14 Administration

Ixazomib (MLN9708) capsules must be administered as intact capsules and are not intended to be opened or manipulated in any way. Capsules should be taken on an empty stomach with approximately 8 oz (1 cup) of water at least 1 hour before or at least 2 hours after food.

Ixazomib should not be taken if the patient has had a serious allergic reaction to boron or boron containing products.

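### After a serious, non-skin Grade 3 allergic reaction attributed to ixazomib alone, Table 8.2 says restart one dose level lower, while Sections 15.14 and 15.16, on their more natural reading, say do not give the drug

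*Combined protocol and SAP*

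**What the plan says.** **Dose-modification rules.** The Other block of Table 8.2 (Section 8.2) covers "Any other non-hematological Grade 3 attributable toxicity except" nausea or emesis without optimal prophylaxis, diarrhea without optimal supportive care, and fatigue. The drug to which the event is attributed is omitted until Grade 1 or baseline. The row then says: "Restart at next lower dose - If a patient is already at the lowest drug level, go to event monitoring". Section 8.11 adds that if a drug was omitted for the rest of a cycle, "then the new cycle will be started with a one-level dose reduction". Section 8.0 sets the force of the tables: "Strictly follow the modifications in this table for the first" two cycles. After that they are guidelines.

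**Drug section.** Section 15.14 states: "Ixazomib should not be taken if the patient has had a serious allergic reaction to boron or boron containing products". Section 15.16 repeats the sentence. Section 1.3 says of ixazomib: "It is the citrate ester of the biologically active boronic acid form".

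**Neighbouring rules.** The only allergic-reaction rows in Section 8 are in Table 8.3 and act on pomalidomide. At Grade 2-3 they omit it and restart one level lower if the reaction settles before Day 15. At Grade 4 they stop pomalidomide and take the patient off all study treatment. Exclusion 3.29e bars patients with a known allergy to a study drug, an analogue or an excipient.

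**The concern.** A site looking up a serious allergic reaction to ixazomib in the dose-modification table finds a rule that fits and says to give the drug again at a lower dose. A site that also reads the drug section finds a warning not to give it. Table 8.2 neither refers to that warning nor exempts allergic reactions from the restart rule. What is at stake is the safety of an individual patient in the period when sites are told to follow the table strictly. The response endpoint, sample size, decision rule and error rates are not affected.

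**Working it through.** The plan states no figure on this point, so the check is a comparison of texts. The case is an allergic reaction that is serious, non-skin, Grade 3 and attributed to ixazomib alone.

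1. **Specific rows of Table 8.2.** The blood-count, rash, Grade 4 skin and neuropathy rows do not fit. No row names allergic reaction.
2. **Table 8.3.** Its allergic-reaction rows act on pomalidomide, to which this event is not attributed.
3. **Catch-all row.** The event is non-hematologic, Grade 3 and attributable, and none of the three exceptions is allergy. The row applies.
4. **Action.** Omit, then restart one level lower. By the dose levels in Section 8.1, 4 mg becomes 3 mg, 3 mg becomes 2.3 mg, and 2.3 mg becomes 2.3 mg on days 1 and 15 only. A patient already at that last level goes to event monitoring, which ends protocol treatment altogether.
5. **Force.** The restart is worded as an instruction. Other Table 8.2 rows are permissive: ixazomib may be restarted after low counts, and restarting may be considered after Grade 4 neuropathy. Section 8.11 points the same way as the catch-all row.
6. **Opposing text.** Ixazomib is a boronic acid compound, so a serious allergic reaction to it is a reaction to a boron-containing product, unless an excipient was the cause. Sections 15.14 and 15.16 then say it should not be taken.

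For this case, steps 4 and 6 cannot both be followed above the lowest dose level.

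**Is the warning about on-study reactions or only about history?** Its tense sets no time limit. In 15.14 it stands under Administration, beside the instructions for taking capsules. Exclusion 3.29e already deals with allergy known at entry, so a history-only reading would largely repeat it. The on-study reading is the more natural one, though it remains an inference.

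**Grade 4.** For a non-skin Grade 4 reaction, the Table 8.2 row tells the investigator to consider stopping ixazomib for good, with the qualification "Exception if the investigator determines the patient is obtaining a clinical benefit". Stopping satisfies both that row and 15.14, so this is a looser fit and not a contradiction.

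**The case against.** The strongest reply is that the boron sentence is a history caution. It sits in the drug monograph, is repeated under drug interactions, and speaks of boron products in general, which suits a question about earlier exposure to bortezomib, another boronic acid analog. On that reading there is no direct conflict. This is possible, but weaker for the reasons given above. It would also leave the protocol warning against ixazomib after a serious reaction to another boron product while ordering a restart after one to ixazomib itself.

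Second, restarting lower is the protocol's own pattern: Table 8.3 does much the same with pomalidomide after Grade 2-3 allergic reactions. That is correct, and a restart rule is not in itself out of line here. But the protocol carries no matching statement that pomalidomide should not be taken after such a reaction, so the inconsistency is specific to ixazomib.

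Third, a reader might infer that the protocol forces re-exposure. It does not. Section 13.4 lets the investigator withdraw a patient for an adverse event or in the patient's best interests, and nothing in Section 8.0 suspends that in cycles 1 and 2. A specific warning can also be held to override a catch-all row. Both points limit the weight of the finding, but 13.4 permits stopping without requiring it, and the table gives no sign that the warning prevails.

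Fourth, the case is narrow. Serious is not the same as severe (Section 10.12), all three drugs are taken on days 1, 8 and 15, so attribution to ixazomib alone will be hard, and Table 8.2 already stops ixazomib for any Grade 4 skin event. This stands, and it keeps the point minor.

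Finally, Section 15.17 refers to the Investigator's Brochure for managing toxicity. The brochure was not available and may deal with hypersensitivity.

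**Conclusion.** The inconsistency is real but minor. In the defined case, the table's default in cycles 1 and 2 is the less safe of two instructions in one protocol. The conclusion rests on three readings: that the boron warning covers reactions during the study, that serious can be taken from the Section 10.421 criteria (15.14 does not define it), and that the reaction is to the drug and not to an excipient. The documents give no rate of hypersensitivity to ixazomib, so no frequency or expected harm can be stated. They do not support a claim that patients will be rechallenged, or that the Grade 4 rule contradicts 15.14.

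**What to change.** Add an ixazomib row for allergic reaction to Table 8.2, cross-referenced to Sections 15.14 and 15.16. State that it overrides the generic Grade 3 and Grade 4 rows and the Section 8.11 restart rule. After an allergic reaction attributed to ixazomib that is serious by the Section 10.421 criteria, or is Grade 4, ixazomib is permanently discontinued with no clinical-benefit exception. Non-serious Grade 3 reactions stay under the existing rule.

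The other drugs may go on under the Section 8.0 note: "If either of pomalidomide or ixazomib is discontinued, the patient can continue on the other drugs". The Grade 4 override is needed for this, because the generic Grade 4 row stops pomalidomide permanently and losing both drugs sends the patient to event monitoring.

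The cost is one table row and a cross-reference at the next amendment. A very few patients would lose ixazomib who might have tolerated a lower dose. Sample size, decision rule and analysis do not change.
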